## 2.2 Summary of Investigational Device

### 2.2.1 Name of the Investigational Device

- XIENCE Xpedition®, XIENCE Xpedition® Small Vessel (SV) and XIENCE Xpedition® LL Everolimus Eluting Coronary Stent System (XIENCE Xpedition Stent System; P110019 / S025, approved on December 21, 2012)
- XIENCE Alpine® Everolimus Eluting Coronary Stent System (XIENCE Alpine Stent System; P110019 / S070; approved on September 3, 2014)
- XIENCE PROX Everolimus Eluting Coronary Stent System^10
- XIENCE PROA Everolimus Eluting Coronary Stent System^11
- XIENCE Sierra Everolimus Eluting Coronary Stent System (XIENCE Sierra Stent System; P110019 / S094; approved on May 22, 2018)

All the above trial devices (hereinafter be called as “XIENCE” in the study) are manufactured by Abbott Vascular. The XIENCE Xpedition, XIENCE Alpine, and XIENCE Sierra EECSS have been approved by the Food and Drug Administration (FDA) and are currently in commercial use in the United States. These stent systems, the XIENCE PROX EECSS and the XIENCE PROA EECSS have also received Conformité Européene (CE) mark and are currently in commercial use in different European countries. Please refer to the Instructions for Use (IFU) for details of each stent system.

 XIENCE PROX is a rebrand of the XIENCE Xpedition Stent System and is only available outside of the U.S.

 XIENCE PROA is a rebrand of the XIENCE Alpine Stent System and is only available outside of the U.S.

### **2.2.2 Intended Indication for Use**

The following is the proposed Intended Use/Indications for Use for the XIENCE Xpedition, XIENCE Alpine and XIENCE Sierra stent system in US as a result of the XIENCE 90 trial:

“The XIENCE [Xpedition/Alpine/Sierra] stent system is indicated for improving coronary artery luminal diameter in patients, including those **at high risk for bleeding** and those with diabetes mellitus, with symptomatic heart disease due to *de novo* native coronary artery lesions (length  $\leq$  32 mm) with reference vessel diameters of  $\geq$  2.25 mm to  $\leq$  4.25 mm. In addition, the XIENCE [Xpedition/Alpine/Sierra] stent system is indicated for treating *de novo* chronic total coronary occlusions.”

### **2.2.3 Description of the Investigational Device**

A full description of XIENCE Xpedition, XIENCE Alpine, XIENCE PROX, XIENCE PROA and XIENCE Sierra stent can be found in the individual stent IFU.

## **3.0 CLINICAL TRIAL/INVESTIGATION FLOW AND FOLLOW-UP SCHEDULE**

### **3.1**

### **3.2 Overall Flow of the Trial and Follow-up Schedule**

The clinical investigation flow is shown in **Appendix V**. Subjects who satisfy eligibility criteria become registered in the study. Subjects have follow-up visits at 3, 6 and 12 months. Assessment of eligibility of DAPT discontinuation will occur at 3-month follow-up.

### **3.3 Measures Taken to Avoid and Minimize Bias**

All the clinical endpoint events will be adjudicated by the Clinical Events Committee (CEC). The CEC is an independent adjudication body comprised of qualified physicians who are not participants in the trial. The CEC will review and adjudicate events as defined in the CEC charter and according to definitions provided in this protocol.

### **3.4 Early Termination of the Clinical Trial**

No formal statistical rule for early termination of the trial is defined.

The Sponsor reserves the right to discontinue the clinical trial/investigation at any stage or reduce the follow up period with suitable written notice to the investigator. Possible reason(s) may include, but are not limited to:

- Unanticipated adverse device effect (e.g., UADE) occurs and it presents an unreasonable risk to the participating subjects.
- Any oversight committee (e.g., Steering/Executive Committee, Data Safety Monitoring Board [DSMB]) makes a recommendation to stop or terminate the trial (such as higher frequency of anticipated adverse device effects).
- Further product development is cancelled.

Should the clinical trial be discontinued by the Sponsor, subjects will be followed up as per routine hospital practice with device related AEs being reported to the Sponsor as per vigilance/commercial reporting requirements.

Should this occur, the investigator shall return all clinical trial/investigation materials to the Sponsor, and provide a written statement as to why the premature termination has taken place to the IRB/EC (if applicable). All applicable Clinical Investigation documents shall be subject to the same retention policy as detailed in **Section 12** Data Handling and Record Keeping.

## **4.0 ENDPOINTS**

### **4.1 Primary Endpoint**

The primary endpoint is a composite rate of all death or all myocardial infarction (MI, modified ARC) from 3 to 12 months. This composite endpoint was chosen because death and MI are important safety endpoints to evaluate short-term DAPT after PCI.

### **4.2 Major Secondary Endpoint(s)**

- Major bleeding rate (BARC type 2-5) from 3 to 12 months
- Stent thrombosis (ARC definite/probable) from 3 to 12 months

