### **4.3 Other Secondary Endpoint(s)**

The following endpoints will be assessed from 3 to 12 months:

- All death, cardiac death, vascular death, non-cardiovascular death
- All MI (modified ARC) and MI attributed to target vessel (TV-MI, modified ARC)
- Composite of cardiac death or MI (modified ARC)
- All stroke, ischemic stroke and hemorrhagic stroke
- Clinically-indicated target lesion revascularization (CI-TLR)
- Clinically-indicated target vessel revascularization (CI-TVR)
- Target lesion failure (TLF, composite of cardiac death, TV-MI and CI-TLR)
- Target vessel failure (TVF, composite of cardiac death, TV-MI and CI-TVR)
- Major bleeding defined by the Bleeding Academic Research Consortium (BARC) type 3-5

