**BLEEDING (Per BARC, Circulation 2011; 123: 2736-2747)**

Bleeding will also be adjudicated per Bleeding Academic Research Consortium (BARC) definitions:

- Type 0: no bleeding
- Type 1: bleeding that is not actionable and does not cause the patient to seek unscheduled performance of studies, hospitalization, or treatment by a healthcare professional; may include episodes leading to self-discontinuation of medical therapy by the patient without consulting a healthcare professional
- Type 2: any overt, actionable sign of hemorrhage (eg, more bleeding than would be expected for a clinical circumstance, including bleeding found by imaging alone) that does not fit the criteria for type 3, 4, or 5 but does meet at least one of the following criteria: (1) requiring nonsurgical, medical intervention by a healthcare professional, (2) leading to hospitalization or increased level of care, or (3) prompting evaluation
- Type 3
  - Type 3a
    - Overt bleeding plus hemoglobin drop of 3 to  $< 5$  g/dL\* (provided hemoglobin drop is related to bleed)
    - Any transfusion with overt bleeding
  - Type 3b
    - Overt bleeding plus hemoglobin drop  $\geq 5$  g/dL\* (provided hemoglobin drop is related to bleed)
    - Cardiac tamponade
    - Bleeding requiring surgical intervention for control (excluding dental/nasal/skin/hemorrhoid)
    - Bleeding requiring intravenous vasoactive agents
  - Type 3c
    - Intracranial hemorrhage (does not include microbleeds or hemorrhagic transformation, does include intraspinal)
    - Subcategories confirmed by autopsy or imaging or lumbar puncture
    - Intraocular bleed compromising vision
- Type 4: CABG-related bleeding
  - Perioperative intracranial bleeding within 48 h
  - Reoperation after closure of sternotomy for the purpose of controlling bleeding
  - Transfusion of  $\geq 5$  U whole blood or packed red blood cells within a 48-h period†
  - Chest tube output  $\geq 2$ L within a 24-h period
- Type 5: fatal bleeding
  - Type 5a
    - Probable fatal bleeding; no autopsy or imaging confirmation but clinically suspicious
  - Type 5b
    - Definite fatal bleeding; overt bleeding or autopsy or imaging confirmation

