1.2 Study Objectives

Primary Objective: to show non-inferiority of the primary endpoint of all death or all MI (modified ARC) from 3 to 12 months following XIENCE implantation in HBR subjects treated with 3-month DAPT compared to a historical control after propensity score adjustment.

Secondary Objective:

- To show superiority of the major secondary endpoint of major bleeding (Bleeding Academic Research Consortium [BARC] type 2-5) from 3 to 12 months following XIENCE implantation in HBR subjects treated with 3-month DAPT compared to a historical control after propensity score adjustment.
- To evaluate stent thrombosis (ARC definite/probable) from 3 to 12 months following XIENCE implantation in HBR subjects treated with 3-month DAPT against a performance goal (PG).

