2.1.4 Hypothesis Testing

Primary endpoint analysis for 3-month DAPT

The XIENCE 90 study is powered based on primary endpoint of Death/MI between 3-month and 12-month follow-up. Death/MI is defined as the composite endpoint of all death or all myocardial infarction (Academic Research Consortium [ARC]). This primary endpoint will be evaluated between XIENCE 90 and XIENCE V USA historical control stratified by propensity score quintiles in the primary analysis population.

The stratified Farrington-Manning method will be performed to test non-inferiority (NI) of 3-month DAPT from XIENCE 90 compared to standard DAPT duration up to 12 months from

XIENCE V USA historical control. [REDACTED]

[REDACTED]

[REDACTED]

[REDACTED]

[REDACTED]

[REDACTED]

[REDACTED]

$$\hat{\delta}_i = p_{it} - p_{ic}$$

$$w_i = \frac{(N_{it} + N_{ic})}{\sum_i (N_{it} + N_{ic})}$$

$$V(\hat{\delta}_i) = \frac{p_{imt}(1-p_{imt})}{N_{it}} + \frac{p_{imc}(1-p_{imc})}{N_{ic}}$$

P_{imt} and P_{imc} are calculated as follows:

$$r_i = N_{it}/N_{ic}$$

$$a1 = - (1 + r_i + p_{ic} + r_i * p_{it} - \delta * (r_i + 2))$$

$$a2 = \delta ** 2 - \delta * (2 * p_{ic} + r_i + 1) + p_{ic} + r_i * p_{it}$$

$$a3 = p_{ic} * \delta * (1 - \delta)$$

$$u = a1**3 / (3 + 3 * r_i) ** 3 - a1 * a2 / (6 * (1 + r_i) ** 2) + a3 / (2 + 2 * r_i)$$

$$v = \text{sign}(u) * \sqrt{a1**2 / ((3 + 3 * r_i) ** 2) - a2 / (3 + 3 * r_i) }$$

$$w = 1 / 3 * (\text{arcos}(-1) + \text{arcos}(u / v ** 3))$$

$$p_{imc} = 2 * v * \cos(w) - a1 / (3 + 3 * r_i)$$

$$p_{imt} = p_{imc} + \delta$$

Major secondary endpoints analyses for 3-month DAPT

If the hypothesis testing for the primary endpoint is successful, the hypotheses testing for the major secondary endpoint #1 will be performed followed by the hypotheses test for the major secondary endpoint #2.

I. Major Secondary Endpoint #1: Bleeding rate (BARC type 2-5) from 3- to 12-month follow-up

The superiority test for the major secondary endpoint #1 will be performed stratified by propensity score quintiles in the primary analysis population.

[REDACTED]

[REDACTED]

[REDACTED]

[REDACTED]

[REDACTED]

II. Major Secondary Endpoint #2: Stent Thrombosis (ARC definite/probable) from 3- to 12-month follow-up

The exact test will be performed for major secondary endpoint #2 in the primary analysis population.

[REDACTED]

This test will be performed if the superiority of major secondary endpoint #1 is established.

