2.2.3 Secondary Endpoint Analyses

Other secondary clinical endpoints will be descriptively analyzed for both the primary analysis population and all registered subjects without propensity stratification.

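### Both documents call two nested endpoints major bleeding: BARC 2-5, which is tested with propensity stratification, and BARC 3-5, for which no stratified analysis is visible

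*Protocol*

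**What the plan says.** - **Label for the tested endpoint.** Protocol 4.2 and SAP 1.3.3.1 name it "Major bleeding rate (BARC type 2-5) from 3 to 12 months". The objective in SAP 1.2, matching Protocol 1.2, is "To show superiority of the major secondary endpoint of major bleeding (Bleeding Academic Research Consortium [BARC] type 2-5) from 3 to 12 months".
- **Same label, narrower range.** Protocol 4.3 and SAP 1.3.3.2 list, among the other secondary endpoints and for the same window, "Major bleeding defined by the Bleeding Academic Research Consortium (BARC) type 3-5".
- **A third label.** The test itself is headed "Major Secondary Endpoint #1: Bleeding rate (BARC type 2-5) from 3- to 12-month follow-up" in SAP 2.1.4. There the bleeding is not called major.
- **Definition of type 2.** Protocol Appendix II describes it as "any overt, actionable sign of hemorrhage" "that does not fit the criteria for type 3, 4, or 5 but does meet at least one of the following criteria". The criteria are non-surgical medical intervention, hospitalisation or more intensive care, or simply an evaluation.
- **Analysis of BARC 2-5.** SAP 2.1.4 and 2.2.2 plan a stratified Farrington-Manning superiority test on propensity quintiles against the XIENCE V USA control, performed only if the primary test succeeds.
- **Analysis of BARC 3-5.** SAP 2.2.3: "Other secondary clinical endpoints will be descriptively analyzed for both the primary analysis population and all registered subjects without propensity stratification". SAP 2.5 likewise limits stratification to the primary and major secondary endpoints. Protocol 9.4.5 speaks of primary and secondary endpoints without the word major, and refers to the SAP for details.

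**The concern.** One term covers two ranges of severity, and the wider range carries the formal claim. If BARC 2-5 succeeds, the objective as worded is met for major bleeding, even if the other endpoint of that name shows no difference. The label matters because the Protocol's rationale (section 2.1) rests on major bleeding as a predictor of mortality, and a result confined to type 2 events would not speak to that argument.

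The natural check is the BARC 3-5 result. But SAP 2.1.3 says the two groups may differ at baseline because they were not randomised, and that is why the tested endpoints are stratified. A BARC 3-5 contrast made without the strata would not be on the same footing as the result it is meant to inform.

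**Working it through.** **1. The plan's own figure.** SAP 1.5 gives 2,000 XIENCE 90 subjects and about 1,150 three-month-clear controls. These cannot be reproduced, because the event rates, margin, power and attrition are not visible. The point does not depend on them.

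**2. How the endpoints relate.** Count each subject once. Every subject with a BARC 3-5 event is also a BARC 2-5 subject, so within each group

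p(2-5) = p(3-5) + p(type 2 only),

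and the difference between groups splits the same way:

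D(2-5) = D(3-5) + D(type 2 only).

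With D(3-5) = 0, the whole tested difference can come from type 2. SAP 2.1.4 weights stratum differences by w_i = (N_it + N_ic) / Σ(N_it + N_ic). These weights do not depend on the endpoint, so the split also holds for the stratified differences, provided all parts use the same strata. It does not hold between a stratified BARC 2-5 difference and a crude BARC 3-5 difference.

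**3. Could the test succeed with D(3-5) = 0?** The inputs are:
- control n = 1,150 (SAP 1.5);
- XIENCE 90 three-month-clear n, not visible: assumed 1,600 to 2,000;
- one-sided alpha 0.025: Protocol 9.4 gives 0.025 for the primary test, none is visible for bleeding, so this is assumed;
- all bleeding rates: assumed;
- an unstratified pooled-variance test as a stand-in for the stratified one.

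Power = Φ[(D − 1.96·s0) / s1], where s0 uses the pooled rate and s1 the separate rates.

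Worked case: 6% versus 4%, n = 1,150 and 1,600.
- Pooled rate = (69 + 64) / 2,750 = 0.0484
- s0 = √[0.0484 × 0.9516 × (1/1,150 + 1/1,600)] = 0.00829
- s1 = √[0.06 × 0.94 / 1,150 + 0.04 × 0.96 / 1,600] = 0.00855
- Power = Φ[(0.02 − 0.01626) / 0.00855] = Φ(0.438) = 0.67

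| BARC 3-5, both groups | Type 2 only, control / XIENCE 90 | BARC 2-5, control / XIENCE 90 | Probability of success |
|---|---|---|---|
| 2% | 4% / 2% | 6% / 4% | 0.67–0.71 |
| 3% | 5% / 3% | 8% / 6% | 0.54–0.58 |
| 2% | 4% / 3% | 6% / 5% | 0.21–0.23 |

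The ranges run over n = 1,600 to 2,000.

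**4. Would a formal BARC 3-5 test be informative?** For an assumed true reduction from 3% to 2%, the same formula gives power of 0.40 to 0.43. That favours an estimate with an interval over a further test.

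**5. Is BARC 3-5 really unadjusted?** SAP 2.2.3 and 2.5 point that way, as does SAP 2.7, which excludes covariate adjustment unless specified. Protocol 9.4.5, read literally, points the other way but defers to the SAP. The SAP probably governs, but the texts do not agree.

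**The case against.** The strongest reply is that no one can mistake which endpoint is tested. The BARC range stands beside the label in the objectives, the endpoint lists and Protocol 9.4.2, and the test heading in SAP 2.1.4 already omits major. BARC 3-5 is prespecified, so a null result there should be visible. Limiting adjustment to the tested hierarchy is a coherent choice, and any composite can succeed on its milder component. All of this stands. It makes the matter one of labelling and interpretation, and testing BARC 2-5 is legitimate.

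A reader might also infer four stronger things that the documents do not support:
- **That BARC 3-5 will certainly be compared with the control, and only crudely.** SAP 2.2.3 does not mention the control, SAP 2.1.2 gives group differences only where specified, and Protocol 9.4.5 can be read as requiring stratification. Parts of SAP 2.1.4, 2.9 and the appendix are redacted, so an adjusted analysis cannot be excluded.
- **That type 2 events depend on how actively each study recorded lesser bleeds.** The visible text does not describe bleeding ascertainment in XIENCE V USA, and XIENCE 90 events go to an independent adjudication committee.
- **That BARC itself reserves the word major for types 3-5.** Appendix II does not use the word. The internal error is one term for two ranges.
- **That success driven by type 2 alone is likely.** The rates above are assumed and show only that it is possible.

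What remains is the double label, the mismatch between the documents, and the absence of a visible stratified BARC 3-5 estimate.

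**Conclusion.** The concern holds as a labelling and interpretation problem. The superiority objective, as worded, could be met by type 2 events alone, and any BARC 3-5 contrast made under the visible SAP text would be crude in a non-randomised comparison. The primary conclusion and the definitions of both endpoints are unaffected, as are error control and sample size.

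The size cannot be fixed from the documents, which show no bleeding rates. In the three assumed scenarios with no BARC 3-5 difference, the chance of declaring superiority runs from 0.21 to 0.71, depending mainly on the assumed type 2 difference. The nesting argument needs none of those assumptions. The statement about crude analysis rests on SAP 2.2.3 prevailing over Protocol 9.4.5 and on nothing contrary in the redacted text. The change is worth making because it is cheap and affects how a headline result will be read.

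**What to change.** 1. **Rename.** Call the tested endpoint BARC type 2-5 bleeding in the objectives (Protocol Summary, Protocol 1.2, SAP 1.2), in Protocol 4.2 and 9.4.2, and in SAP 1.3.3.1. The heading in SAP 2.1.4 already does nearly this. The term major bleeding then refers only to BARC 3-5.
2. **Reconcile.** Make Protocol 9.4.5 agree with SAP 2.2.3 and 2.5 on which secondary endpoints are evaluated after stratification.
3. **Add a supportive estimate.** Beside the BARC 2-5 test, report the BARC 3-5 difference with its 95% CI, using the same propensity quintiles and weights, and mark it as untested. The type 2 contribution then follows by subtraction.

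The cost is wording in both documents and one more run of an existing program. No new data, alpha or subjects are needed. The downside for the sponsor is a possibly less favourable headline.

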### **4.3 Other Secondary Endpoint(s)**

The following endpoints will be assessed from 3 to 12 months:

- All death, cardiac death, vascular death, non-cardiovascular death
- All MI (modified ARC) and MI attributed to target vessel (TV-MI, modified ARC)
- Composite of cardiac death or MI (modified ARC)
- All stroke, ischemic stroke and hemorrhagic stroke
- Clinically-indicated target lesion revascularization (CI-TLR)
- Clinically-indicated target vessel revascularization (CI-TVR)
- Target lesion failure (TLF, composite of cardiac death, TV-MI and CI-TLR)
- Target vessel failure (TVF, composite of cardiac death, TV-MI and CI-TVR)
- Major bleeding defined by the Bleeding Academic Research Consortium (BARC) type 3-5

## **5.0 SUBJECT SELECTION AND WITHDRAWAL**

### **5.1 Subject Population**

This trial will register male and female HBR subjects from the general interventional cardiology population who satisfy the inclusion and exclusion criteria. [REDACTED] Subjects must meet all clinical and angiographic eligibility criteria and provide written informed consent prior to conducting any trial-specific procedures not considered standard of care.

#### **5.1.1 Medicare Population**

This trial will register male and female HBR subjects including those age 65 years old and older, i.e., Medicare age. The study results are expected to be generalizable to the Medicare population. It is not expected that the results will be any different for Medicare patients than for non-Medicare patients.

## 5.2 Subject Screening and Informed Consent

### 5.2.1 Subject Screening

Subjects admitted for a percutaneous coronary artery revascularization procedure must be screened for clinical trial eligibility by a member of the clinical trial team (physician and/or research coordinator) previously trained to the clinical trial protocol and if applicable will be entered into a site specific screening log.

Subjects meeting the general inclusion and exclusion criteria will be asked to sign an informed consent. Pre-procedure (or baseline) imaging will be used for the final assessment of subject eligibility (details are described in **Section 5.3**). Subjects who do not satisfy the angiographic inclusion and exclusion criteria are considered screen failures and will not be registered and proceed further in the trial. These subjects will be entered into the screening log. Also, the reason for screen failure as well as supporting data will be entered into the log.

Patient data will be collected following registration into the trial/investigation.

### 5.2.2 Informed Consent

The Investigator or designee, who has been trained on the Protocol, will explain the nature and scope of the trial, potential risks and benefits of participation, and answer questions for the subjects. All subjects (or legally authorized subjects' representatives if applicable) must sign and date (and time, as per applicable local standards) the Institutional Review Board (IRB)/Ethics Committee (EC) approved informed consent (ICF) prior to any clinical trial/investigation-specific procedures. All efforts should be made to consent a subject prior to index procedure. However, it is acceptable for the subject to provide consent prior to hospital discharge and up to 3 days after the index procedure, only if the site confirms that the protocol required DAPT regimen is site's standard of care. If staged procedures are needed for a subject, the site may consent the subject after the initial procedure.

Obtaining the consent and provisioning of a copy to the subject, along with the date and time must be documented in the subject's medical records. The ICF must be signed by the investigator or designate (if allowed per country specific regulations). In addition, the signed informed consent must be kept in the subject's medical records/research chart and a copy must be given to the subject or the legally authorized representative.

In addition, an authorization for use and disclosure of the subject's protected health information, in accordance with the Health Insurance Portability and Accountability Act (HIPAA), must be obtained from the subject or their legally authorized representative (US only).

For Live cases at congresses the patients need to sign a specific Live Case ICF, approved by the IRB/EC. The investigator must notify Abbott Vascular prior to performing a Live Case. FDA approval is also required for a live case conducted in US.

